12.5 Analysis of secondary endpoints/estimands

12.5.1 Efficacy and/or pharmacodynamic endpoint(s)

FAS will be used to analyze durability, functional and anatomical outcomes.

To evaluate the anatomical outcomes of brolocizumab in all patients and per randomized arm in the core study

- Change in CSFT from extension baseline to Week 52 and Week 56
- Number of visits with presence of IRF and/or SRF, and sub-RPE fluid in the central subfield as assessed by SD-OCT at Week 52 and Week 56

To assess the durability of brolocizumab in all patients and/or per randomized arm in the core study

- Duration of the last interval with no DA up to Week 56
- Duration of the maximal intervals with no DA up to Week 56
- Change of the duration of last interval with no DA between extension baseline and Week 56

To assess the functional outcomes of brolocizumab per randomized arm in the core study

- Change in BCVA from extension baseline to Week 52 and Week 56

Counts and proportions for the endpoints describing durability, tolerability and anatomical outcomes (i.e. number of visits with presence of IRF and/or SRF) will be accompanied by two-sided 95% CI inferred based on binomial distribution for each endpoint and two-sided 95% simultaneous CIs inferred using the Goodman method ([Goodman 1965](#)). The Goodman method is used for obtaining simultaneous confidence intervals (might be better than single binomial confidence intervals) for the parameters of a multinomial distribution, for example for a multinomial endpoint (4-week interval, 8-week interval, 12-week interval, 16-week interval, and 20-week interval). These analyses will be performed for all participants.

For the analyses of functional and anatomical outcome (i.e. change in CSFT) the 95% CI will be inferred based on ANOVA analyses.

12.5.2 Safety endpoints

The following endpoints assess the safety of brolocizumab

- Occurrence of Ocular and Non-ocular AEs up to Week 56

For all safety analyses, the FAS will be used. All listings and tables will be presented in all participants.

Safety summaries (tables, figures) include only data from the on-treatment period with the exception of baseline data which will also be summarized where appropriate (e.g. change from baseline summaries). In addition, a separate summary for death will be provided. In particular, summary tables for adverse events (AEs) will summarize only on-treatment events, with a start date during the on-treatment period. A separate summary table will be provided for AEs of study eye, fellow eye and non-ocular AEs.

The on-treatment period lasts from the date of first administration of study treatment to 30 days after the last administration of study treatment (EOT) or EOS whichever is the latest.

Adverse events

Treatment emergent AEs are defined as AEs which start on or after the time of the first injection of study treatment in this extension study and until the patient exits the study. AEs which start prior to the date/time of the first injection of study treatment in this extension study will be listed only. Treatment emergent AEs occurring during the last 6 months of the core study, for the same set of participants included in the extension study safety set will be presented. All treatment emergent SAEs/AEs as documented in the core study will be listed as medical history.

The number (and percentage) of participants with treatment emergent adverse events (events started after the first dose of study medication or events present prior to start of the extension study but increased in severity based on preferred term) will be summarized in the following ways:

- by primary system organ class and preferred term.
- by primary system organ class, preferred term and maximum severity.
- by Standardized MedDRA Query (SMQ) and preferred term.

Separate summaries will be provided for study medication related adverse events, death, serious adverse events, other significant adverse events leading to discontinuation.

[figure not shown]
The number (and proportion) of participants with adverse events of special interest will be summarized.

A participant with multiple adverse events within a primary system organ class is only counted once towards the total of the primary system organ class.

Adverse events which will be counted for a specific treatment period (i.e. baseline to Week 52) are those which are treatment-emergent. These events are those with an onset after the start of the treatment period, or which were present prior to the start of the treatment period but increased in severity, changed from being not suspected to being suspected of study drug relationship, or developed into SAEs after the start of the treatment period.

Vital signs

Clinically relevant abnormalities in vital signs data will be listed by participant and visit/time and if ranges are available, abnormalities will be flagged. Summary statistics will be provided by visit/time.

12.7 Interim analyses

There is no interim analysis planned for the study.

150	9.6%	15.2%	15.1%	11.3%	13.2%
120	10.9%	17.1%	16.9%	12.7%	14.9%
100	12.0%	18.8%	18.6%	14.0%	16.3%

Table 12-4 95% Confidence Interval for BCVA change assuming SD of the change is 13.

N of participants completing the extension study	95% Confidence Interval of BCVA change assuming the observed change is -1.
503	(-2.1, 0.14)
447	(-2.2, 0.21)
391	(-2.3, 0.29)
447	(-2.2, 0.21)
398	(-2.3, 0.28)
348	(-2.4, 0.37)
391	(-2.3, 0.29)
348	(-2.4, 0.37)
304	(-2.5, 0.47)
250	(-2.6, 0.62)
200	(-2.8, 0.81)
170	(-3.0, 0.97)
150	(-3.1, 1.1)
120	(-3.4, 1.4)
100	(-3.6, 1.6)

13 Ethical considerations and administrative procedures

13.1 Regulatory and ethical compliance

This clinical study was designed and shall be implemented, executed and reported in accordance with the ICH Harmonized Tripartite Guidelines for Good Clinical Practice, with applicable local regulations (including European Directive 2001/20/EC, US CFR 21), and with the ethical principles laid down in the Declaration of Helsinki.

13.2 Responsibilities of the investigator and IRB/IEC

Before initiating a trial, the investigator/institution must obtain approval/favorable opinion from the Institutional Review Board/Independent Ethics Committee (IRB/IEC) for the trial protocol, written informed consent form, consent form updates, participant recruitment procedures (e.g., advertisements) and any other written information to be provided to participants. Prior to study start, the investigator is required to sign a protocol signature page confirming his/her agreement to conduct the study in accordance with these documents and all of the instructions and

procedures found in this protocol and to give access to all relevant data and records to Novartis monitors, auditors, Novartis Quality Assurance representatives, designated agents of Novartis, IRBs/IECs, and regulatory authorities as required. If an inspection of the clinical site is requested by a regulatory authority, the investigator must inform Novartis immediately that this request has been made.

13.3 Publication of study protocol and results

The protocol will be registered in a publicly accessible database such as clinicaltrials.gov and as required in EudraCT. In addition, after study completion (defined as last patient last visit) and finalization of the study report the results of this trial will be submitted for publication and posted in a publicly accessible database of clinical trial results, such as the Novartis clinical trial results website and all required Health Authority websites (e.g. Clinicaltrials.gov, EudraCT etc.).

For details on the Novartis publication policy including authorship criteria, please refer to the Novartis publication policy training materials that were provided to you at the trial investigator meetings.

13.4 Quality Control and Quality Assurance

Novartis maintains a robust Quality Management System (QMS) that includes all activities involved in quality assurance and quality control, to ensure compliance with written Standard Operating Procedures (SOPs) as well as applicable global/local GCP regulations and ICH Guidelines.

Audits of investigator sites, vendors, and Novartis systems are performed by auditors, independent from those involved in conducting, monitoring or performing quality control of the clinical trial. The clinical audit process uses a knowledge/risk-based approach.

Audits are conducted to assess GCP compliance with global and local regulatory requirements, protocols and internal SOPs, and are performed according to written Novartis processes.

14 Protocol adherence

This protocol defines the study objectives, the study procedures and the data to be collected on study participants. Additional assessments required to ensure safety of participants should be administered as deemed necessary on a case by case basis. Under no circumstances including incidental collection is an investigator allowed to collect additional data or conduct any additional procedures for any purpose involving any investigational drugs under the protocol, other than the purpose of the study. If despite this interdiction prohibition, data, information, observation would be incidentally collected, the investigator shall immediately disclose it to Novartis and not use it for any purpose other than the study, except for the appropriate monitoring on study participants.

Investigators ascertain they will apply due diligence to avoid protocol deviations. If an investigator feels a protocol deviation would improve the conduct of the study this must be considered a protocol amendment, and unless such an amendment is agreed upon by

Novartis and approved by the IRB/IEC and Health Authorities, where required, it cannot be implemented.

Table 2-1	Primary and sensitivity estimands.....	16
Table 2-2	Critical changes in vital signs	22
Table 3-1	Duration of intervals as estimated based on simulation studies.....	24
Table 3-2	Duration of intervals as estimated based on simulation studies and width of 95% confidence Interval	25
Table 3-3	95% Confidence interval for BCVA change assuming SD of the change is 13.....	25
Table 5-1	Patient classification.....	30
Table 5-2	Non-protocol deviations (analysis restrictions)	31

List of abbreviations

Abbreviation	Definition
AE(s)	Adverse Event(s)
AESI	Adverse Event of Special Interest
ANOVA	Analysis of Variance
AR	Analysis Restrictions
ATC	Anatomical Therapeutic Chemical
BCVA	Best-Corrected Visual Acuity
CI(s)	Confidence Interval(s)
CFP	Color Fundus Photography
CM	Concomitant Medication
CNV	Choroidal Neovascularization
COVID-19	Coronavirus disease 2019
CRF	Case Report/Record Form (paper or electronic)
CSR	Clinical Study Report
CRS	Case Retrieval Sheet
CSFT	Central Subfield Thickness
DA	Disease Activity
CSR	Clinical Study Report
DAA	Disease Activity Assessment
eCRF	Electronic CRF
EOS	End of Study
EOT	End of Treatment
FA	Fluorescein Angiography
FAS	Full Analysis Set
ICF	Inform Consent Form
LLN	Lower Limit of Normal
IRF	Intraretinal Fluid
IOP	Intraocular Pressure
LOCF	Last Observation Carried Forward
LSM	Least-Squares Mean
MedDRA	Medical dictionary for regulatory activities
MMRM	Mixed Model for Repeated Measures
nAMD	neovascular Age-related Macular Degeneration
OCT	Optical Coherence Tomography
PD(s)	Protocol Deviation(s)
PDS	Programming Datasets Specifications
PPS	Per-Protocol Set
PT	Preferred Term
RPE	Retinal Pigment Epithelium
SAE	Serious Adverse Event

Abbreviation	Definition
SAP	Statistical Analysis Plan
SD-OCT	Spectral Domain Optical Coherence Tomography
SE	Standard Error
SMQ	Standardized MedDRA Query
SOC	System Organ Class
SRF	Subretinal Fluid
TFL	Tables, Figures and Listings
TtC	Treat-to-Control
ULN	Upper Limit of Normal
VEGF	Vascular Endothelial Growth Factor
WHO	World Health Organization

1 Introduction

This document describes the detailed statistical methodology to be used for the Clinical Study Report (CSR) of the TALON-extension study CRTH258A2303E1; a 56-week, phase IIIb/IV, open-label, one-arm extension study to assess the efficacy and safety of brolocizumab 6 mg in a Treat-to-Control (TtC) regimen with maximum treatment intervals up to 20 weeks for the treatment of participants with neovascular age-related macular degeneration (nAMD) who have completed the CRTH258A2303 (TALON-core) study.

The content of this Statistical Analysis Plan (SAP) is based on amended protocol version 02. All decisions regarding the final analysis, as defined in this SAP document, will be made prior to final database lock and unblinding of the study data.

CSR deliverables (shells for tables, figures, listings [TFLs]) and further programming specifications will be described in the TFL shells and Programming Datasets Specifications (PDS), respectively.

1.1 Study design

The study is a 56-week open-label, multi-center, one-arm extension study in participants with nAMD who have completed the TALON core study.

Approximately 250 participants from the core study (CRTH258A2303, TALON) will enter this extension study. The primary analyses will be conducted when all ongoing participants have completed their Week 56 visit and after the database lock.

[figure not shown]
1.2 Study objectives and endpoints

The study objectives and corresponding endpoints as specified in the protocol are provided in [Table 1-1](#).

Table 1-1 Study objectives and endpoints

Objectives	Endpoints	Analysis
Primary objectives	Endpoints for primary objectives	Analysis

 To evaluate the extended durability of brolocizumab in a TtC regimen with respect to the duration of treatment intervals at Week 56 To evaluate the functional outcomes of brolocizumab in a TtC regimen with respect to average change in BCVA at Week 52 and Week 56 	
 Duration of the last interval with no DA up to Week 56 Change in BCVA from extension baseline at Week 52 and Week 56 	Section 2.5
Secondary objectives	Endpoints for secondary objectives	Analysis

 To evaluate the anatomical outcomes of brolocizumab in all patients and per randomized arm in the core study 	
 Change in CSFT from extension baseline to Week 52 and Week 56 Number of visits with presence of IRF and/or SRF, 	Section 2.6

Objectives	Endpoints	Analysis

 To assess the durability of brolocizumab in all patients and/or per randomized arm in the core study 	
 and sub-RPE fluid in the central subfield, as assessed by SD-OCT at Week 52 and Week 56 Duration of the last interval with no DA up to Week 56 Duration of the maximal intervals with no DA up to Week 56 Change of the duration of last interval with no DA between extension baseline and Week 56 	

 To assess the functional outcomes of brolocizumab per randomized arm in the core study 	
 Change in BCVA from extension baseline to Week 52 and Week 56 	

 To assess the safety of brolocizumab 	
 Occurrence of Ocular and Non-ocular AEs up to Week 56 	Section 2.7

2 Statistical methods

All analyses described in the SAP will be performed by Novartis. Any additional (or other) data analysis carried out independently by the investigators should be submitted to Novartis before publication or presentation.

2.1 Data analysis general information

Categorical data will be presented as frequencies and percentages. For continuous data, n, mean, standard deviation, median, minimum, and maximum will be presented. For selected parameters, 25th and 75th percentiles will also be presented (when applicable).

2.1.1 General definitions

All the definitions, e.g. baseline, on-treatment period, are referring to the current extension study unless otherwise stated, e.g. baseline of the core study.

Study treatment is defined as brolocizumab 6 mg/0.05 mL.

Date of first administration of study treatment is defined as the first date when a non-zero dose of study treatment is administered and recorded on the case report form (CRF) dose administration page. The date of first administration of study treatment will also be referred to as start of study treatment.

Date of last administration of study treatment is defined as the last date when a non-zero dose of study treatment is administered and recorded on the CRF dose administration page. The last administration of study treatment will also be referred as end of treatment (EOT).

Study day will be calculated as:

- The date of the event (visit date, onset date of an event, assessment date etc.) – treatment start date + 1, if event is on or after the treatment start date;
- The date of the event (visit date, onset date of an event, assessment date etc.) – treatment start date, if event precedes the treatment start date.

Baseline/Day 1 is the end of study (EOS)/Week 64 of the core study.

On-treatment period is defined from Day 1 of the study to 30 days after the last administration of study treatment (i.e. EOT) or end of study (EOS), whichever is the latest.

Treatment interval is defined as the time period from one injection until the next injection. In this study, treatment intervals of q4w, q8w, q12w, q16w and q20w, meaning that there are 4, 8, 12, 16 and 20 weeks between 2 injections, are of special interest. The last (treatment) interval at Week X is referred to the last complete interval where injections at both ends of the interval have occurred on or before Week X. The last interval with/without disease activity is referred to the last interval with/without disease activity as observed at the end of the interval.

The first treatment is defined by the treatment interval of the core study. For example, a patient who started a 16-weeks interval at Week 56 of the core study will have the first treatment 8 weeks after the start of the extension study (i.e. 8 weeks after Week 64).

Participants will be assessed for eligibility based on inclusion and exclusion criteria for the extension study at the baseline visit.

The study day will be displayed in data listings. All data from scheduled and unscheduled visits will be analyzed based on “Week XX” recorded in the CRF (except for baseline), unless otherwise stated.

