8.1 Screening

8.1.1 Information to be collected on screening failures

Participants who sign an informed consent form and subsequently found to be ineligible will be considered a screen failure. The reason for screen failure should be entered on the applicable Case Report Form. The demographic information, informed consent, and Inclusion/Exclusion pages must also be completed for screen failure participants. No other data will be entered into the clinical database for participants who are screen failures, unless the participant experienced a serious adverse event during the evaluation of eligibility (see SAE [Section 10.1.3](#) for reporting details).

Participants who sign an informed consent and are considered eligible but fail to be started on treatment for any reason will be considered an early terminator. The reason for early termination should be captured on the appropriate disposition Case Report Form.

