2.7 Safety analyses

The following endpoint will be used to assess the safety and tolerability of brolocizumab

- Occurrence of Ocular and Non-ocular AEs up to Week 56.

The primary population for safety analyses is the FAS. Additionally, the Enrollment Set will be used to summarize pre-treatment AEs and all AEs that occur during the extension study. All listings and tables will be presented for all participants.

Safety summaries (tables, figures) will include only data from the baseline of the extension study, which is also EOS/Week 64 of the core study.

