2.7.1 Adverse events (AEs)

Note that AEs which start during the core study and end prior to the core EOS are not recorded on the Medical History eCRF, nor the Adverse Event eCRF. These AEs are considered as the Medical History in the extension study, hence the data from the core AE will be programmatically merged with the Medical History eCRF. Therefore, these events are not included in any AE summaries or listings but will be included in Medical History listings.

Treatment-emergent Adverse Events: The primary summaries of AEs will be based on treatment-emergent adverse events (TEAE). A TEAE is defined as any AE that develops on/after the first injection of study treatment or any event already present that worsens following the first injection of study treatment.

The number (and percentage) of participants with TEAEs will be summarized separately for ocular (study eye and fellow eye) and non-ocular in the following ways:

- Overall summary of subjects with death, any TEAE, any severe TEAE, any study treatment related TEAE, any TEAE leading to study treatment discontinuation, any treatment-emergent serious AE (TESAE), any study treatment related TESAE;
- TEAE, TESAE by primary SOC and PT;
- TEAE by primary SOC, PT, and maximum severity
- TEAE by Standardized MedDRA Query (SMQ) and PT;
- TEAEs related to study treatment by primary SOC and PT;
- TEAEs leading to study treatment discontinuation by primary SOC.

A subject with multiple AEs within a primary SOC is only counted once towards the total of the SOC.

Ocular TEAE in the study eye with occurrence greater than or equal to 1% and non-ocular TEAE with occurrence greater than or equal to 2% will be summarized by PT.

Pre-treatment Adverse Events: In addition to TEAEs, AEs which start on/after day 1 of the extension study and prior to the date/time of the first injection of the study treatment in the extension study will be summarized using number and percentage of patients by ocular (study eye and fellow eye)/non-ocular, primary SOC and PT using the Enrollment Set.

Study-emergent Adverse Events: All AEs that occur during the on-treatment period (defined in Section 2.1.1) will be summarized separately for ocular (study eye and fellow eye) and non-ocular events using the Enrollment Set in the following ways:

- AEs by primary SOC and PT;
- SAEs by primary SOC and PT;
- SAEs by primary SOC and PT, and maximum severity;
- Study treatment related SAEs, by primary SOC and PT

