2.7.2 Deaths

On-treatment deaths and all deaths including those that occurred outside the on-treatment period will be summarized by primary SOC and PT. A listing will also be provided.

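### The SAP starts the on-treatment period at Day 1 (core Week 64) instead of the first extension injection, contrary to the protocol and without declaring the change

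*SAP*

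**What the plan says.** **Protocol.** Section 12.5.2 states: "The on-treatment period lasts from the date of first administration of study treatment". The period ends 30 days after the last administration or at end of study, whichever is later. AE summaries are confined to events starting in that period, AEs before the first extension injection are only to be listed, and the FAS is the set for all safety analyses. Section 12.1 reserves the Enrolled Analysis Set for disposition and pre-treatment AEs.

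**SAP.** Section 2.1.1 states: "On-treatment period is defined from Day 1 of the study to 30 days after the last administration of study treatment". The end of the period matches the protocol; the start does not, because the same section says: "Baseline/Day 1 is the end of study (EOS)/Week 64 of the core study". Three outputs use this period by name:

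- Section 2.7.1, study-emergent tables on the Enrollment Set: "All AEs that occur during the on-treatment period (defined in Section 2.1.1").
- Section 2.7.2: "On-treatment deaths and all deaths including those that occurred outside the on-treatment period".
- Section 2.7.5.1, summary statistics for vital signs.

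The registry tables in 2.7.1 still carry a placeholder that offers on-treatment and treatment-emergent as alternatives. The serious-event table refers to a safety set, which SAP 2.2 does not define. SAP Section 4 lists only added endpoints measured from the core baseline.

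**The concern.** An on-treatment label tells the reader that the participant had already received the study drug. Under the SAP definition, an event can carry that label before any extension injection. The study treatment is brolucizumab, but participants enter from either core arm. For someone who received aflibercept in the core study, an event in the gap follows aflibercept and precedes any study brolucizumab. SAP 2.7 presents the safety tables for all participants together, so a reader could not see this.

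The SAP is also inconsistent within itself. Its study-day formula counts from treatment start ("treatment start date + 1, if event is on or after the treatment start date"), so an event in the gap has a negative study day and is nevertheless on-treatment. In 2.7.1 the same AE meets the definition of a pre-treatment AE and also falls in the on-treatment window of the study-emergent tables.

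**Working it through.** **1. Reproduce the documents' examples.** Gap = week of last core injection + planned interval − 64.

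- SAP 2.1.1 (16-week interval started at core Week 56): 56 + 16 − 64 = 8 weeks.
- Protocol 6.7.2 (12-week interval from core Week 60): 60 + 12 − 64 = 8 weeks.

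Both agree with the documents.

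**2. Range of the gap.** Core intervals run from 8 to 16 weeks (Protocol 1.1). Week 60 is the last core injection week in the protocol's example.

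| Last core injection | Interval (weeks) | Gap (weeks) | Share of 56 weeks |
|---|---|---|---|
| Week 56 | 8 | 0 | 0% |
| Week 60 | 8 | 4 | 7% |
| Week 60 | 12 | 8 | 14% |
| Week 56 | 16 | 8 | 14% |
| Week 60 | 16 | 12 | 21% |

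The notes to Protocol Figure 3-1 also mention core Week 62. If an injection was given then on a 16-week interval, the gap is 62 + 16 − 64 = 14 weeks (25%). These are shares of calendar time, not errors in a reported rate.

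**3. Can Day 1 mean the first injection?** No. SAP 2.1.1 ties Day 1 to core Week 64, and 2.7.1 defines pre-treatment AEs as those between day 1 and the first injection.

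**4. Which outputs move.**

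- *Study-emergent AE and SAE tables, including treatment-related SAEs:* they move, because window and set are both stated.
- *Deaths:* the definition makes a death in the gap on-treatment. Someone who dies in the gap before any extension dose is outside the FAS, and SAP 2.7.2 names no set. On the Enrollment Set the death would be shown as on-treatment; on the FAS it would appear in neither death summary.
- *Vital signs:* only readings at visits inside the gap are affected.
- *Registry tables:* undetermined until the placeholder is resolved.
- *TEAE, TESAE and AESI tables:* they do not move, because they count from the first injection.

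**5. Direction of any effect on percentages.** The documents give neither the incidence nor the fraction never dosed, so this is an illustration under a constant hazard. Let p be the incidence over 56 weeks, g the gap, u the fraction of the Enrollment Set never dosed (contributing g weeks each), and h = −ln(1 − p)/56.

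- TEAE on the FAS = 1 − exp(−h(56 − g)).
- Study-emergent on the Enrollment Set = (1 − u)p + u(1 − exp(−hg)).

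With p = 30%:

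| g (weeks) | u | TEAE on FAS | Study-emergent on Enrollment Set | Difference (points) |
|---|---|---|---|---|
| 8 | 0 | 26.3% | 30.0% | +3.7 |
| 8 | 5% | 26.3% | 28.8% | +2.4 |
| 8 | 10% | 26.3% | 27.5% | +1.2 |
| 4 | 10% | 28.2% | 27.3% | −0.9 |
| 0 | 10% | 30.0% | 27.0% | −3.0 |

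Differences are taken before rounding. Pre-dose events raise the numerator and never-dosed participants enlarge the denominator, so the sign is not fixed.

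**The case against.** The strongest reply is that the main safety results are sound. SAP 2.7 keeps the FAS as the primary safety population, and 2.7.1 bases the primary AE summaries on events from the first injection. That stands, and it limits the point to secondary outputs.

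The second reply is that SAP 2.7 presents the Enrollment Set tables as an additional account of all AEs during the extension. For that purpose a Day 1 start and an all-enrolled set belong together, and some overlap with the pre-treatment table is expected. Forcing these tables onto the FAS from first injection would largely duplicate the TEAE tables and lose events in participants never dosed. This also stands. What it does not justify is calling the window on-treatment, or applying it to deaths, vital signs and possibly registry tables.

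A reader might infer that Enrollment Set percentages are diluted because the set includes people who cannot contribute events. The documents do not support this. Protocol 8.1.1 says "No other data will be entered into the clinical database for participants who are screen failures", but the sentence goes on to exempt serious events during the eligibility evaluation. Eligible participants who never start treatment are early terminators rather than screen failures, and AEs are recorded from consent (Protocol 10.1.1).

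A reader might also take the SAP 2.7 sentence "Safety summaries (tables, figures) will include only data from the baseline of the extension study" as a decision to report baseline data only. The same section sets AEs up to Week 56 as the endpoint, so this is a drafting slip.

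**Conclusion.** The contradiction is real, undeclared and confined to the start of the period. As written, the SAP rule labels up to about 12 weeks before the first extension injection as on-treatment: 8 weeks in both documents' examples, and none for a participant injected at baseline. The 12-week figure assumes a last core injection at Week 60 on a 16-week interval; a Week 62 injection would make it 14.

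The study-emergent AE and SAE tables are certainly affected, vital signs in a small way, deaths depending on an unstated set, and registry tables possibly. The primary TEAE, TESAE and AESI summaries are not affected.

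The stronger reading, that safety percentages are too low by some stated fraction, should not be drawn. The never-dosed fraction is unknown, and under the illustrative model with an 8-week gap the net effect is upward. For former brolucizumab participants the gap follows core-study brolucizumab, so the mislabelling matters most for those coming from aflibercept.

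**What to change.** 1. In SAP 2.1.1, start the on-treatment period at the date of first administration in the extension, as in Protocol 12.5.2, and reconcile Day 1 with the study-day formula.
2. Use that period for on-treatment deaths and vital signs, on the FAS. In 2.7.2, also name the set for the all-deaths summary so that a death before the first dose is not lost.
3. Specify the registry tables as treatment-emergent on the FAS, replacing the placeholder and the undefined safety set.
4. If the all-AE summary from Day 1 on the Enrollment Set is kept, define its window under a separate name such as study period, state its denominator, and record it in SAP Section 4 as a departure from Protocol 12.1 and 12.5.2.
5. Correct the SAP 2.7 sentence to follow the protocol: on-treatment data, with baseline data where appropriate.

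The cost is SAP wording and one derived date in the programs. No new data are needed. The all-AE summary need not be given up, only relabelled and declared.
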